2.9 Pharmacokinetic endpoints

Not applicable.

[figure not shown]
2.10 PK analyses

[figure not shown]
PK sampling will be performed at visits 205, 299/301, and 303. Blood samples will be collected at time-points: 0h (pre-dose) and approximately 1h, 2h, 4h, and 6h post dose.

Plasma concentration of LIK066 and scheduled time from dosing will be summarized by treatment and visit/sampling time point. PK parameters (Cmax, Tmax, AUClast, AUC0-t) will be listed and summarized. Descriptive statistics includes n, mean, standard deviation, minimum, median, maximum, coefficient of variation (%) for arithmetic mean, geometric mean, and coefficient of variation (%) for geometric mean.

Concentrations below the lower limit of quantification (LLOQ) will be treated as zero in summary statistics and for PK parameter calculations. A geometric mean will not be reported if the dataset includes zero values.

Individual LIK066 plasma concentration data will be listed by treatment, subject, and visit / sampling time point.

2.12 Biomarkers

Serum samples for bone and renal biomarkers, and urine bone biomarkers will be collected from subjects who participate in the PK substudy. Biomarkers are collected at Visit 201, 205, 299/301, 303, and 399. Data will be analyzed based on SAF.

Table 2-9 Biomarkers

Category	Parameter(s)
Bone biomarkers	β -c-terminal telopeptide (β -CTX1), serum procollagen type 1 N-propeptide (sP1NP), intact parathyroid hormone (iPTH), 25-hydroxy vitamin D, 1,25 dihydroxy vitamin D, osteocalcin, estradiol, calcium, magnesium, phosphates
Renal biomarkers	Serum cystatin, urinary cystatin C/creatinine ratio (spot urine)

[figure not shown]
Week 24 analysis

Summaries of absolute values and change from BL in each of the bone, renal, and inflammatory biomarkers by treatment group and visit will be presented using statistics: n, mean, SD, median, minimum, maximum, Q1, Q3, geometric mean and coefficient of variation. Figures will be

produced to visually show the mean values by visit over 24 weeks of treatment in Epoch 3 for each treatment group.

End of study analysis

The absolute values and change from Week 24 in each of the bone, renal and inflammatory biomarkers will be similarly summarized and depicted as for the Week 24 analysis.

2.14 Interim analysis

Not applicable.

3 Sample size calculation

The study planned to randomize approximately 432 subjects in total, allocated in the ratio of 1:1:1:1:1:2:1:1:1:2 to the following 10 Epoch 3/Epoch 4 treatment groups:

1. placebo/placebo
2. placebo/LIK066 25 mg qd
3. LIK066 2.5 mg qd/25 mg qd
4. LIK066 10 mg qd/25 mg qd
5. LIK066 50 mg qd/25 mg qd
6. LIK066 150 mg qd/25 mg qd
7. LIK066 2.5 mg bid/35 mg qd
8. LIK066 5 mg bid/35 mg qd
9. LIK066 25 mg bid/35 mg qd
10. LIK066 50 mg bid/35 mg qd

This randomization scheme implies that the Epoch 3 treatment and Epoch 4 treatment for a specific subject is determined simultaneously at randomization visit. The randomization will be stratified by subjects' glycemic status at screening: normoglycemic, dysglycemic and T2DM.

As the dose-response assessment is conducted in qd and bid regimens separately (while an overall family-wise type I error is controlled at a one-sided significance level of 2.5 %), power calculation was done for testing dose-response signal by regimen as well. Table 3-1 summarizes the average power and the lowest power across the candidate dose response shapes in Figure 2-1 by regimen, under different scenarios with the assumptions on effect size of body weight loss (percent change from BL) for the dose of maximum effect, and the related standard deviations.

Note that a dose-response signal is detected (ie the primary objective is met) as long as either of the dose-response signals for the two regimens is detected. Therefore, the overall study power is at least the maximum of the powers between two regimens for each scenario considered.

Table 3-1 Power for detecting a significant dose response signal*

Dose regimen	Effect size for best dose	SD	Average power**	Minimum power†
Qd	5 %	5.5 %	99.99 %	99.98 %
	5 %	6.5 %	99.71 %	99.57 %
	6 %	5.5 %	99.99 %	99.99 %
	6 %	6.5 %	99.99 %	99.98 %
Bid	5 %	5.5 %	99.16 %	95.84 %
	5 %	6.5 %	96.50 %	86.79 %
	6 %	5.5 %	99.90 %	99.43 %
	6 %	6.5 %	99.28 %	96.36 %

Dose regimen	Effect size for best dose	SD	Average power**	Minimum power†
--------------	---------------------------	----	-----------------	----------------

* Assumes 432 subjects in LIK066 and placebo arms with effective sample size of 367 subjects due to an effect of missing data equivalent to 15 % fewer subjects. Calculations were performed using the DoseFinding package in R.

† Power for a significant dose-response contrast test across all scenarios within each regimen in Table 3-1. The candidate model #5 in bid regimen has the lowest power.

It was assumed that the effect of losses to follow-up is equivalent to effectively having 15 % fewer subjects than randomized, even if the multiple imputation approach used to handle missing values should be able to recover some information for such subjects.

4 Change to protocol specified analyses

In protocol section 9.5.1.1 change from BL at Week 24 in hsCRP was listed as one of the secondary efficacy variables, and this has been modified to percent change from BL at Week 24 in hsCRP in \log_{10} transformation in the SAP.

5 Appendix

5.1 Imputation rules

5.1.1 Study drug

Any partial dates will be imputed as the earlier day of

- The last day in the month and
- The end day of the corresponding epoch

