2.1.1 General definitions

Baseline (Week 0) for Week 24 analysis and overall analysis including both Epoch 3 and Epoch 4 data will be defined as the last measurement before or at the randomization visit. Baseline for End of study analysis including Epoch 4 data only will be defined as the last measurement in Epoch 3.

The first day of administration of randomized study treatment (first dose) is defined as Day 1 for the study. If the date of first administration is missing, then randomization date will be used as Day 1.

All other study days will be labeled relative to Day 1. For event dates on or after Day 1, study day for a particular event date is calculated as [Date of event] – [Date of first dose] + 1. For the dates before Day 1, study day for an event date is calculated as [Date of event] – [Date of first dose]. Duration of an event will be calculated as [Event end date] – [Event start date] + 1. The descriptor “Day 0” will not be used.

For Week 24 analysis, the treatment groups presented are:

- LIK066 2.5 mg qd
- LIK066 10 mg qd
- LIK066 50 mg qd
- LIK066 150 mg qd
- LIK066 2.5 mg bid
- LIK066 5 mg bid
- LIK066 25 mg bid
- LIK066 50 mg bid
- Placebo
- Total (if applicable)

For End of study analysis, unless specified otherwise, the following treatment grouping strategy will be used, expressed as per the Epoch 3 treatment/Epoch 4 treatments a subject is assigned to at randomization:

- LIK066 qd any dose/LIK066 25 mg qd, shortened as LIK066 qd/LIK066 25 mg qd
- LIK066 bid any dose/LIK066 35 mg qd, shortened as LIK066 bid/LIK066 35 mg qd
- Placebo/LIK066 25 mg qd
- Placebo/placebo, shortened as Placebo
- Total (if applicable)

For End of study AE listings, the 10 randomized treatments will be used, as shown in Section 1.1 study design, along with the additional two pooled groups:

- LIK066 qd any dose/LIK066 25 mg qd, shortened as LIK066 qd/LIK066 25 mg qd
- LIK066 bid any dose/LIK066 35 mg qd, shortened as LIK066 bid/LIK066 35 mg qd
- Total (if applicable)

For overall analysis including both Epoch 3 and Epoch 4 treatment, the 10 randomized treatment grouping strategy will be used, as shown in Section 1.1 Study design.

For the Week 24 analyses, data collected up to the end date of Epoch 3 will be included. For AEs and concomitant medications, this means that events with start dates prior to the end of Epoch 3 dates are included.

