2.2 Analysis sets

Screened set (SCR): the SCR consists of all subjects who signed the ICF.

Randomized set (RAN): All subjects who have received a randomization number, regardless of receiving trial medication.

Run-in set (RUN): All subjects who enter the run-in epoch.

Full analysis set (FAS): the FAS comprises all subjects to whom study treatment has been assigned, except those who are not qualified for randomization but were inadvertently randomized into the study and did not take any study drug. Following the intent-to-treat principle, subjects will be analyzed according to the treatment assigned to at randomization.

Safety set (SAF): the SAF includes all subjects who received at least one dose of study medication. Subjects will be analyzed according to treatment received. Note that the safety set allows the inclusion of non-randomized subjects who received the study drug in error.

Per-protocol set (PPS): the PPS is a subset of the FAS. It consists of all randomized subjects in the FAS who have been exposed to study medication for at least 22 weeks and have no major protocol deviations (PDs) affecting the primary endpoint analysis.

Randomized set – Epoch 4 (RAN-Epoch 4): all randomized subjects who have been assigned a treatment in Epoch 4.

Full analysis set – Epoch 4 (FAS-Epoch 4): all RAN-Epoch 4 subjects, excluding those who did not take any Epoch 4 study medication.

Safety set – Epoch 4 (SAF-Epoch 4): all SAF subjects who received at least one dose of Epoch 4 study medication.

Protocol deviations will be pre-specified prior to un-blinding treatment codes for analyses. See Appendix Table 5-2 and Table 5-3 for list of protocol deviations and criteria that lead to exclusion from analysis sets, and related rules of exclusion criteria of analysis sets.

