2.4 Treatments (study treatment, rescue medication, concomitant therapies, compliance)

2.4.1 Study treatment / compliance

Week 24 analysis

The duration of double-blind treatment exposure in Epoch 3 will be summarized by treatment group both descriptively in days (mean, standard deviation, minimum, Q1, median, Q3, and maximum) and by duration category in weeks (≤ 2 , $>2-4$, $>4-8$, $>8-12$, $>12-16$, $>16-20$, $>20-24$, and >24) for the SAF.

- Duration of exposure (days) = last dose date of Epoch 3 – first dose date + 1
- Duration of exposure (weeks) = (last dose date of Epoch 3 – first dose date + 1)/7

Overall subject-years on-treatment in Epoch 3 will be reported by each treatment group.

- Overall subject-years on-treatment = sum of duration of treatment exposure (in days) from all subjects / 365.25

The duration of double-blind treatment exposure excluding treatment interruptions in Epoch 3 will also be summarized descriptively and by duration categories as above.

- Duration of exposure excluding treatment interruptions (days) = last dose date of Epoch 3 – first dose date + 1 – number of days of treatment interruption

Treatment interruptions will be considered as following:

- For BID doses – patients taking 0 tablets for both morning and evening doses,
- For QD doses – patients taking 0 tablets for the morning dose,
- For Placebo – patients taking 0 tablets for both morning and evening doses.

Number and percentage of subjects with treatment interruption and permanent treatment discontinuations in Epoch 3 will be provided by reason for treatment interruption or discontinuation.

Duration of treatment interruption, frequency and duration of the PD after meal dose intake will also be summarized as appropriate.

End of study analysis

The duration of Epoch 4 will be summarized by treatment group both descriptively in days and by duration-category in weeks (≤ 4 , $>4-12$, $>12-24$, and >24) for subjects in the safety set who enter the study Week 24 to Week 48 period (Epoch 4), respectively.

- Epoch 4 duration of exposure (days) = last dose date – first dose date of Epoch 4 + 1
- Epoch 4 duration of exposure (weeks) = (last dose date – first dose date of Epoch 4 + 1)/7

Duration of treatment interruption, frequency and duration of PD after meal dose intake will also be summarized as appropriate.

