2.8.1 Adverse events (AEs)

Week 24 analysis

A treatment-emergent AE for Week 24 is defined as any AE in Epoch 3 that develops after initiation of the study treatments or any event already present that worsens following exposure to the study treatment. Following the definition, AEs occurring after treatment discontinuation will also be considered as treatment-emergent AEs. Treatment emergent AEs will be summarized for Week 24 analysis. The number and percentage of subjects having AEs will be summarized by system organ class, preferred term, and treatment group. Unless otherwise specified, primary system organ will be sorted alphabetically and, within each primary system organ class, the preferred terms will be sorted in descending order of frequency in the investigational study drug arm (LIK066 150 mg qd). If a patient reported more than one AE with the same preferred term, the AE will be counted only once. If a patient reported more than one AE within the same primary system organ class, the patient will be counted only once at the system organ class level. The number and percentage of subjects having AEs will be summarized by system organ class, preferred term, treatment group, and subgroups of interest (glycemic status, age group and sex) as well.

The most frequent AEs ($\geq 2\%$ in any treatment group) will be presented by preferred term in descending order of frequency in the investigational study drug arm, LIK066 150 mg qd.

AEs will also be presented by greatest severity. If a patient reported more than one AE with the same preferred term, the highest severity will be presented. All AEs will be summarized by highest severity, primary system organ class, preferred term, and treatment. If a patient reported

more than one AE within the same primary system organ class, only one AE will be counted for that patient at the highest severity level in the total row for each primary system organ class. Missing severity will be assumed to be severe in the summary table.

AEs suspected to be related to study drug, serious AEs, fatal AEs, and AEs leading to study drug discontinuation, study drug interruption will be summarized by presenting number and percentage of patients with an event by primary system organ class, preferred term, and treatment.

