5.4 Rule of exclusion criteria of analysis sets

Protocol deviations are identified prior to clinical database lock/unblinding and entered into a dedicated data panel as part of the locked database. Details are provided in the PD Specs and Edit Checks tab of LIK066B2201 Edit Check Specification document.

The protocol deviations resulting in exclusion of subjects from an analysis population are outlined in Table 5-1 below.

Table 5-2 Protocol deviations that cause subjects to be excluded

Deviation ID	Description of Deviation	Exclusion in Analyses
INCL01	Informed consent not obtained	Excluded from SCR, RUN, RAN, FAS, SAF, and PPS
TRT19	Subject withdrew consent and not discontinued from the study	Data collected after withdrawal of IC, excluded from FAS and SAF
TRT34	Patients mis-randomized in IRT	Excluded from FAS and PPS
INCL03	BMI not within range or BMI missing	Excluded from PPS
EXCL04	Subject taking prohibited medication	Excluded from PPS
EXCL05	Patient with a history of malignancy	Excluded from PPS
EXCL06	Pregnant patient	Excluded from PPS
EXCL08	Use of active weight-loss medications	Excluded from PPS
EXCL09	Bariatric surgery	Excluded from PPS
EXCL10b	Not compliant with lifestyle intervention	Excluded from PPS
EXCL19	Substances or alcohol abuse	Excluded from PPS
TRT06	Study treatment adjusted	Excluded from PPS
TRT11	Study treatment unmasked and subject not discontinued from the study	Excluded from PPS
TRT15	Use of prohibited medication and not discontinued from the study	Excluded from PPS
TRT22	Use of another investigational drug while on study	Excluded from PPS
TRT35	Study medication taken after the morning or evening meal	Excluded from PPS
TRT28	Misdispensed medication and taken by patient	Excluded from PPS

[figure not shown]
Table 5-3 Subject Classification

Analysis Set	PD ID that cause subjects to be excluded	Non-PD criteria that cause subjects to be excluded
SCR	INCL01	Not having screening epoch disposition page

Analysis Set	PD ID that cause subjects to be excluded	Non-PD criteria that cause subjects to be excluded
RUN	INCL01	Not in ENR; Not having run-in epoch disposition page
RAN	INCL01	Not randomized
FAS	INCL01, TRT19, TRT34	Not in RAN;
PPS	INCL01, INCL03, EXCL04, EXCL05, EXCL06, EXCL08, EXCL09, EXCL10b, EXCL19, TRT06, TRT11, TRT15, TRT22, TRT35, TRT 28, and TRT34	Overall exposure on DB medication < 22 weeks unless premature discontinuation due to adverse events
SAF	INCL01, TRT19	No double-blind study drug taken

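### SAP 5.1.1 applies a month-end rule to every partial study-drug date, so a partial Epoch 3 first-dose date would be set up to 30 days late

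*SAP*

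**What the plan says.** SAP 5.1.1 is the only imputation rule for study-drug dates: "Any partial dates will be imputed as the earlier day of" two days. The first bullet reads "The last day in the month and" and the second "The end day of the corresponding epoch". Start and stop dates are not distinguished, whereas SAP 5.1.2 (adverse events) and 5.1.3 (concomitant medication) each give separate start and end rules.

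SAP 2.1.1 has one rule specific to the first dose: "If the date of first administration is missing, then randomization date will be used as Day 1". It does not say whether a partial date counts as missing.

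The first-dose date feeds several definitions:

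- Day 1 and all study days (SAP 2.1.1).
- Epoch 3 exposure (SAP 2.4.1): "Duration of exposure (days) = last dose date of Epoch 3 – first dose date + 1".
- Treatment-emergent status (SAP 2.8.1): "any AE in Epoch 3 that develops after initiation of the study treatments". On-treatment status uses treatment start and end dates.
- The per-protocol set (PPS). SAP 2.2 requires that subjects "have been exposed to study medication for at least 22 weeks". Table 5-3 in SAP 5.4 excludes subjects with "Overall exposure on DB medication < 22 weeks unless premature discontinuation due to adverse events".

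**The concern.** Taking the latest possible day is a sensible choice for a last dose. Applied to a first dose it gives the latest possible Day 1. Read literally, the two rules also produce an odd ordering: a first-dose date about which nothing is known becomes the randomization date, while one known to the month can land weeks later.

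The time lost is the first days or weeks of dosing. Protocol 3.3 and 3.6 report that gastrointestinal events became less frequent over time in most subjects, and SAP 2.8.1.1 tabulates diarrhea in windows that begin at 0 to under 2 weeks. Early tolerability data would therefore be the part affected. A late first dose also shortens exposure, which can push a fully treated subject below the PPS threshold.

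**Working it through.** There is no stated figure to reproduce. The check is calendar arithmetic on the SAP's own formulas. 'Partial' is taken to mean that month and year are known and the day is not.

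**Inputs.** Epoch 3 lasts 24 weeks = 168 days (Protocol 3.1.2). The PPS threshold is 22 weeks = 22 × 7 = 154 days (SAP 2.2, Table 5-3). Exposure = last dose − first dose + 1 (SAP 2.4.1). Imputed first dose = earlier of month end and epoch end (SAP 5.1.1). Epoch end is about 24 weeks after the first dose, so for a completer the cap never applies to a first-dose date.

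**Shift.** Month end minus true day runs from 0 days to 30 days (the 1st of a 31-day month). With start days spread evenly over a 365-day year (an assumption), the mean is (7 × 465 + 4 × 435 + 378)/365 = 5373/365 = 14.7 days.

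**One completer.** First dose 3 May, recorded only as May, becomes 31 May: 28 days late. Credited exposure is 168 − 28 = 140 days = 20.0 weeks, below 154. Table 5-3 makes an exception only for discontinuation due to adverse events, so a completer gets none.

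**Threshold.** 168 − 154 = 14 days of tolerance, so a shift of 15 days or more fails. In a 31-day month, day 16 gives 153 days (fails) and day 17 gives 154 (passes). Failing start days are 1–16 in the seven 31-day months, 1–15 in the four 30-day months and 1–13 in a 28-day February: 112 + 60 + 13 = 185 of 365 = 51%.

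| True exposure (days) | Failing start days | Share, given a partial date |
|---|---|---|
| 167 | 197 of 365 | 54% |
| 168 | 185 of 365 | 51% |
| 169 | 173 of 365 | 47% |
| 175 | 101 of 365 | 28% |

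**Adverse events.** True first dose 5 August, complete onset date 10 August: study day 10 − 5 + 1 = 6. With the first dose imputed to 31 August, SAP 2.1.1 gives 10 − 31 = −21, which is pre-treatment.

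**Partial onset dates.** Under SAP 5.1.2, an onset known only to the treatment-start month is set no earlier than the day after the imputed start, so it stays post-treatment unless the event ended earlier.

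**Epoch 4 first dose.** Epoch 4 exposure is last dose − first Epoch 4 dose + 1, so a late start understates it. SAP 2.8.1 defines new treatment-emergent events in Epoch 4 from the start of Epoch 4, so their status does not change.

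**Interruption start.** SAP 2.4.1 subtracts interruption days from exposure. A start moved to month end leaves fewer days to subtract, so exposure net of interruptions is overstated.

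**The case against.** **Intent.** An epoch-end cap makes sense only for a stop date, so 5.1.1 was probably written with stop dates in mind. SAP 2.1.1 is specific to the first dose. If 'missing' there includes 'partial', the Epoch 3 problem disappears. This reading is plausible, and the two sections do not contradict each other in terms. But 5.1.1 says 'any' partial date, and nothing in the SAP says which rule prevails. Separate groups perform the Week 24 and final analyses (Protocol 5.4, SAP 5.6.1), so the boundary should be written down.

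**Rarity.** Protocol 5.5.4 has study drug taken after visit procedures on visit days and dosing recorded on a dedicated form. The randomization system assigns the first pack at Visit 201 (Protocol 5.3), and data pass automatic validation (Protocol 8.2). Partial first-dose dates should be few. This stands.

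**Per-protocol reading.** Table 5-3 speaks of 'overall' exposure, and SAP 2.4.1 uses that word for Epochs 3 and 4 together. On that reading a 48-week completer keeps at least 336 − 30 = 306 days and passes. This stands as a condition: the loss arises if the rule is applied to Epoch 3 exposure, as is natural for the Week 24 analysis, or if the subject stops at Week 24.

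**Stronger inferences that the documents do not support.** A reader might infer that about half the subjects would leave the PPS; the 51% applies only to 168-day completers who have a partial date. A reader might also infer that new Epoch 4 events would be reclassified, or that a late interruption start cuts exposure. The first does not follow from the Epoch 4 definition, and the second runs in the opposite direction.

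**Conclusion.** The point holds as a gap in the text with a wrong result if followed literally. A partial Epoch 3 first-dose date would be placed 0 to 30 days late. Adverse events with a complete onset date inside that gap would be counted as pre-treatment, and Epoch 3 exposure would be understated by the same number of days.

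PPS exclusion of a completer further requires that the 22-week rule be read on Epoch 3 exposure. For 168 days of true exposure it then needs a shift of 15 days or more. The shares of 51% (168 days) and 28% (175 days) assume evenly spread start days and are conditional on a partial date; they are not expected exclusion rates. The documents give no count of such dates.

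A reader might infer that the main result is at risk. It is not: the primary analysis uses the full analysis set as randomized with Week 24 weight, and the on-treatment supportive analysis is keyed to the final intake date. The PPS serves a sensitivity analysis (SAP 2.5.4). The correction is still worth making, because the rule governs Day 1, exposure and adverse-event status and costs almost nothing to repair.

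**What to change.** - Restrict SAP 5.1.1 to last-dose and interruption-end dates.
- State that the 2.1.1 rule also covers a partial Epoch 3 first-dose date: use the randomization date when it agrees with the known month, otherwise the earliest date in that month not before randomization.
- Use the analogous rule with the Visit 301 date for the Epoch 4 first dose.
- For a partial interruption start, use the earliest date consistent with the record.

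If the first dose was taken on the day of randomization, the completer in the example returns to 168 days (24.0 weeks), passes the 22-week rule, and has no post-dose event before Day 1. The cost is a few SAP sentences and the matching program change. No new data are needed. Reporting the number of partial start dates would show whether the rule mattered.
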